THE OVERALL HYPOTHESIS TO BE TESTED IN THIS TRIAL is that the early introduction of combination therapy of corticosteroids and either MTX or CsA will prove more effective and safe than corticosteroids alone in the treatment of JDM.

Trial Design and Duration. Two-year single-blind (assessor blinded to treatment arm of subject), randomised, actively controlled, multi-centre, international prospective, superiority trial of different combination of drugs. Patients will be then followed for up to 5 years for the evaluation of long term morbidity and mortality.

Dose Regimen (see figure 1):

3 daily pulses of intravenous (iv) methylprednisolone (30 mg/kg/pulse max 1 g/pulse) followed by randomisation into one of these 3 groups.

Induction of remission

Group 1 prednisone or equivalent (PDN): PDN 2 mg/kg/day (see below for rules regarding PDN administration);

Group 2 PDN+cyclosporine A (CsA): PDN 2 mg/kg/day + CsA 5 mg/kg/day in 2 oral doses.;

Group 3 PDN + methotrexate (MTX): PDN 2 mg/kg/day + MTX 15-20 mg/m² once per week. Patients treated with MTX will receive concomitant folic or folinic acid according to the attending physician decision.

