Suggested PDN administration for all 3 groups: From a survey conducted in USA high dose corticosteroids are used as initial treatment of choice by 76% of the paediatric rheumatologists (personal communication), justifying therefore the inclusion of this arm in the trial. After randomisation all patients in the 3 groups will receive 2 mg/kg/day of PDN or its equivalents. In the first month, PDN will be administered in 3 divided daily doses (oral preferentially). Starting at month 2, PDN will be administered orally in a single daily dose in the morning, and tapered, if allowed by clinical status, by 0,25 mg/kg every week to reach a daily dose of 1 mg/kg/day at the end of month 2. Then until the end of month 6, PDN should be tapered, if allowed by clinical status, to reach a daily dose of 0.2 mg/kg at the end of month 6. Starting at month 7 all patients will receive a daily dose of 0.2 mg/kg/day, that will be maintained until the end of month 12. Starting at month 13 the PDN dose will be reduced to 0.1 mg/kg/day for further 6 months and then to every-other-day regimen at a dose of 0.1 mg/kg/day until month 24. If the patient will reach clinical remission before month 24, PDN will be withdrawn earlier than the suggested schedule of PDN administration. For prevention of osteoporis patients can be treated with calcium and vitamin D supplementation according to the attending physician decision.

Suggested CsA administration: CsA will be administered orally at 4-5 mg/kg/day in 2 divided dose. If serum creatinine will rise > 30% of baseline value CsA dose will be reduced by 1-2 mg/kg/day (depending on severity) for 1 month. If after 1 month serum creatinine will return < 30% of baseline value CsA can be continued at the same lower dose. If after 1 month serum creatinine will remain > 30% of baseline value stop CsA for 1 month and then check again serum creatinine: a) if serum creatine after 1 month stop of CsA return within 10% of baseline value CsA can be restarted at 3 mg and increased to the maximum tolerated dose (depending on serum creatinine level); b) if serum creatine after 1 month stop of CsA still remain > 10% of baseline value CsA stop definitively.

[figure not shown]

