Suggested MTX administration: MTX will be administered parenterally (subcutaneously, intramuscularly) at 15-20 mg/m² once per week. In case of MTX related toxicity (eg transaminase increase) stop MTX for 2 weeks and if adverse event disappear start again at 10 mg/m² once per week and increase of 2.5 mg/m² once per week every week until the maximum tolerated dose (max 20 mg/m² once per week). If adverse event persist stop methotrexate. Patients treated with MTX will receive concomitant folic (1 mg/day except the day of MTX administration) or folinic acid (25-50% of the MTX dose in mg; to be administered the day after MTX administration) according to the attending physician decision.

Long term follow up after month 24 until month 60. All patients will be followed for a total of 5 years for the assessment of long term morbidity and mortality rate. After month 24 treatment will be left open to the physician decision based on the clinical status of the patient.

Important: Medications will be supplied by the pharmacy of the participating centre and covered with the standard way of reimbursement in each participating country.

Subject Population. Newly diagnosed and untreated children with probable or definite diagnosis of JDM according to Bohan and Peter Criteria (12;13).

Figure 1: JDM study design

Efficacy Parameters:

Primary Outcome Measures after 6 months of treatment. According to the PRINTO definition of improvement for JDM, patients will be considered responders to therapy if they will demonstrate at least 20% improvement in at least 3 core set variables with no more than 1 of the remaining variables, (muscle strength excluded), worsened by > 30% (4).

The PRINTO JDM core set variables (4) are:

- 1) muscle strength by the mean of the Childhood Myositis Assessment Scale (CMAS);
- 2) physician's global assessment of disease activity on a 10 cm VAS ;
- 3) global disease activity assessment by the mean of the Disease Activity Index (DAS);
- 4) parent's/patient's global assessment of overall well-being on a 10 cm VAS;
- 5) functional ability assessment by the mean of the Childhood Health Assessment Questionnaire (CHAQ)
- 6) health-related quality of life assessment.

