Primary Outcome Measures after 24 months of treatment: a) time to clinical remission on medication defined as normal muscle strength and physician global assessment of disease activity equal to 0; b) time to flare of the disease defined as at least 20%, worsening from the previous evaluation value in 2 of any 6 JDM core set measures with no more than 1 of the remaining improved by more than 30% (muscle strength excluded).

Effectiveness: the rate of retention on treatment will be used as main measure of effectiveness.

Secondary Outcome Measures. Change over time in the individual components of the JDM core set of variables; time to muscle enzymes normalisation; frequency of drop-out of suggested steroids use; frequency of drop-out for inefficacy of treatment.

Safety Parameters.

- 1) Incidence of adverse events (AE):
 - a) Number of patients discontinuing trial due to on-therapy conditions and AE possibly, probably, or definitely related to the experimental therapy, and listing of AE that cause discontinuation.
 - b) Number of patients for whom the dosage was lowered, or withheld temporarily, due to AE, and listing of the specific AE that caused such action.
 - c) Complete list of AE by system.
- 2) Incidence of clinically significant changes in laboratory parameters.
- 3) Drop out rate due to toxicity.

Inclusion Criteria. Each patient must meet all the following criteria in order to participate in this trial:

- 1) Newly diagnosed and untreated children (only treatment with 1 NSAID is allowed and/or prednisone >1 mg/kg/day for no more than 1 month from diagnosis) with probable or definite diagnosis of JDM according to the Bohan and Peter criteria (12;13). If a muscle biopsy will be performed (optional) it will be read by the pathologists of the participating centres (light and immunofluorescence). Slides of paraffin-embedded sections from all patients will be re-viewed by a blinded myopathologist at PRINTO.
- 2) Age at enrolment \leq 18 years.
- 3) Female of child-bearing potential must have a negative pregnancy test at the beginning of the trial, and then every 3 months. If sexually active, they must agree to use adequate contraception, throughout study participation, and must have no intention of conceiving during the course of the study. Post-pubertal males must have no plans to father a child during the study and agree to use adequate birth control methods if sexually active.

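### Safety counts 1a and, on one reading, 3 record toxicity by exit from the trial, so permanent loss of CsA or MTX in a child who stays on PDN is isolated by no safety measure

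*Protocol*

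**What the plan says.** The Safety Parameters section of the protocol defines these measures:

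- 1a: "Number of patients discontinuing trial due to on-therapy conditions and AE possibly, probably, or definitely related to the experimental therapy", with a listing of the events.
- 1b: "Number of patients for whom the dosage was lowered, or withheld temporarily, due to AE", with a listing of the events.
- 1c: "Complete list of AE by system".
- 2: incidence of clinically significant laboratory changes.
- 3: "Drop out rate due to toxicity".

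Permanent stops of a single drug are foreseen elsewhere. Under Suggested CsA administration the sequence begins "If serum creatinine will rise > 30% of baseline value CsA dose will be reduced by 1-2 mg/kg/day (depending on severity) for 1 month". If creatinine stays high, a one-month stop and a re-check follow. The sequence can end with creatinine that "still remain > 10% of baseline value CsA stop definitively". Under Suggested MTX administration, toxicity leads to a two-week stop, with a restart if the event resolves; otherwise, "If adverse event persist stop methotrexate". Neither section says whether the child then leaves the trial.

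Dropout Criteria lists non-compliance and enrolment in another trial, but not toxicity. Procedures in the Case of Adverse Events gives two options for an event that does not resolve: drop the child from the trial, or repeat the procedure with another drug. Withdrawal From the Trial leaves removal to the attending physician's clinical judgement.

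**The concern.** The trial objective includes safety and tolerability, and the hypothesis is that the combinations "will prove more effective and safe than corticosteroids alone in the treatment of JDM". Having to give up CsA or MTX for good because of toxicity is direct evidence on that question. Yet 1a depends on the child leaving the trial, and 3 may do so too. If the child stays on PDN, the combination's figure in 1a does not move.

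Only Groups 2 and 3 have an added drug that can be lost while PDN continues, so the gap bears mainly on those arms. The main effectiveness measure, retention on treatment, does not settle the matter. The protocol does not say whether a child randomised to a combination but now on PDN alone counts as retained.

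**Working it through.** The plan gives no rate of permanent CsA or MTX stops, so there is no figure of its own to reproduce on this point. The only planning input needed is the arm size: 34 evaluable per arm with 15% drop-out gives 34 / (1 − 0.15) = 40, as stated.

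**Step 1. Can the situation arise?** Yes. The CsA and MTX sections end in a stop of that drug alone, toxicity is not a dropout criterion, and removal is a clinical decision. The general AE procedure does not foresee this outcome, since for a persisting event it offers only exit or a trial of another drug. The protocol is thus inconsistent on whether the child stays.

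**Step 2. Which counts record the child?**

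| Child | 1a | 1b | 3 |
|---|---|---|---|
| CsA stopped for good by the creatinine route, stays | No | Yes: dose lowered first, then a one-month stop | No, if drop-out means leaving the trial |
| MTX stopped for good after the two-week stop, stays | No | Yes, if the two-week stop is read as a hold (the natural reading) | Same |
| Add-on stopped for good at once, outside the written steps, stays | No | No | Same |
| Add-on stopped for a related AE, leaves the trial | Yes | As above | Yes |

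Measure 1c records the event but not the action on the drug. Measure 2 records a creatinine or transaminase change but not the stop. In 1b, a child who lost the drug permanently counts the same as one who missed two weeks and resumed.

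The meaning of drop-out in measure 3 is open. Dropout Criteria uses the idea for leaving the trial, whereas Secondary Outcome Measures also uses it for departure from the suggested steroid schedule.

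**Step 3. Size, by assumption.** Let n = 40 per arm, q = the proportion permanently stopping the add-on for toxicity, and f = the share of these who stay. Children absent from 1a (and from 3 on the trial-exit reading) = n × q × f per arm.

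- q = 5%, f = 1: 40 × 0.05 = 2 per arm, 4 over both combination arms.
- q = 15%, f = 1: 40 × 0.15 = 6 per arm, 12 over both.
- f = 0.5: 1–3 per arm, 2–6 over both.

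The number absent from 1b is zero on the CsA creatinine route, and zero on the MTX route if the two-week stop counts as a hold.

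**The case against.** The strongest reply is that little is lost. The written routes pass through a reduction or a hold, so these children enter 1b. The event appears in 1c, and the named triggers (creatinine, transaminases) fall under measure 2. The general AE procedure may lead to exit from the trial, which feeds 1a and 3. Retention may register the loss, and its derivation could be left to the SAP. Adverse events are reported descriptively, so no test or power figure depends on these counts. Keeping a child who stopped MTX in the MTX arm is simply the stated intention-to-treat emphasis.

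Much of this stands. A reader might infer that such children are missing from every drug-stopping count; the CsA and MTX sequences do not support that, because of 1b. A reader might also infer a bias strictly in favour of the combinations. That is not shown either. The protocol does not say that a Group 1 child who stops PDN for toxicity leaves the trial, and children on two drugs have more doses that can be lowered or held, so 1b can count against the combinations.

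The reply does not remove the gap. Merging permanent with transient dose changes hides the more serious outcome, and 1c and 2 do not record what was done with the drug. The protocol itself words 1a by trial exit, so this is a matter of stated text and not of detail left to the SAP.

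**Conclusion.** The point holds in limited form. A child who permanently stops CsA or MTX for toxicity and remains on PDN is absent from 1a, is absent from 3 if drop-out means leaving the trial, and appears in 1b only among temporary holds and reductions. No safety measure isolates permanent loss of the randomised add-on.

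This can understate treatment-limiting toxicity, mainly in Groups 2 and 3. The illustration of 2–6 children per arm rests on an assumed 5–15% stop rate and on all such children staying; half that number follows if half stay. The documents give neither quantity. Efficacy tests and sample size are unaffected. What suffers is the description of tolerability, which is part of the objective and of the hypothesis.

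**What to change.** Keep 1a and 1b as they are. Add a count, by arm and by drug, of patients permanently discontinuing any assigned drug (PDN, CsA or MTX) due to AE, whether or not they stay in the trial. Base measure 3 on that event. State one rule for how loss of an assigned drug counts towards retention on treatment, and apply it in all three arms.

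Separately, reconcile Suggested CsA administration, Suggested MTX administration, Dropout Criteria and Procedures in the Case of Adverse Events on whether a child who permanently stops one drug remains in the trial. Which clinical rule applies is for the sponsor and investigators.

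The cost is slightly more tabulation. The action taken on each drug must be read from the weekly dose diary or the AE form; the protocol describes the form as holding severity and relationship, so a field for action taken may be needed. The combinations' toxicity figure may look slightly less favourable.

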- 4) Ability to comply with the entire study procedures, ability to communicate meaningfully with the investigational staff, competence to give written informed consent; to be applied to the parents and/or patients, as appropriate
- 5) Duly executed, written, informed consent obtained from the parents/patient.

Exclusion Criteria. Any of the following will exclude a patient from this trial:

- 1) Neutrophil count $<1,500/\text{mm}^3$ and/or platelet count $<50,000/\text{mm}^3$
- 2) Demonstration of cutaneous or gastrointestinal ulceration of JDM related pulmonary disease or cardiomyopathy at the time of diagnosis.
- 3) History of poor compliance.
- 4) Evidence of current use of alcohol or illicit drugs abuse.
- 5) Live vaccines not allowed during the entire duration of the trial.

Dropout Criteria. Patients will be considered "treatment failures", and dropped from the trial but included in efficacy analysis, if any of the following will occur during the active period of the trial.

- 1) Non compliance with study medication administration
- 2) Enrolment in other therapeutic trials.

Feasibility study for sample size calculation: from the analysis of the 295 patients with JDM enrolled in a previous PRINTO study (EU contract QLG1-CT-2000-00514) (4) it can be inferred that the network can enrol in a 2 years frame up to 190 children with less than 12 months disease duration (of whom 140 with disease duration less than 6 months).

Sample size calculation for superiority trial. We used the PRINTO JDM definition of improvement (see previous section "definition for primary outcome") (4) for sample size calculation for superiority trials.

We carried out sample size calculations based on the information obtained from a study on JDM patients conducted by PRINTO with a previous grant (contract EU contract QLG1-CT-2000-00514). In the study a total of 284 JDM patients with a mean age at onset of 7.6 years (Standard Deviation [SD] 3.9) the observed improvement rate was 83% after 6 months of therapy with PDN combined with MTX or CSA. We estimated that the group treated only with PDN will have a response rate equal to 53%.

Using the sample size calculation for superiority trials and considering a drop out rate of 15%, a sample size of **40 patients in each group for a total of 120 patients**, will be required. The trial will have 0.8 power for comparisons of the combined treatment arms (PDN+MTX or PDN+CSA) to the reference treatment arm (PDN alone).

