If enrolment will proceed faster than expected we will collect 54 patients per arm for a total of 162 patients, 0.9 power, 0.05 type I error.

Below is a table with different sample size calculations, using different levels of power.

| Variable | PDN treatment | delta | alfa | Power | N per arm | Drop-out N/(1-0.15) |
|-----------------|---------------|-------|------|-------|-----------|---------------------|
| PRINTO JDM def. | 53 | 30% | 0.05 | 0.8 | 34 | 40 |
| PRINTO JDM def. | 53 | 30% | 0.05 | 0.9 | 46 | 54 |

Procedures in the Case of Adverse Events. In the event of clinical or laboratory AE, the attending physician should make the clinical decision as to which medication is most likely the cause of the AE. The suspected medication (experimental or allowed) should be stopped or dosage reduced for 1 or 2 weeks. If the AE disappears or significantly ameliorates then the medication will be reinstated. If the AE does not disappear the physician will either drop the patient from the trial, or repeat the procedure with one of the remaining drugs. The drug that was initially discontinued (experimental or allowed) may be reinstated (as deemed appropriate by the attending physician), once it has been shown not to be the cause of the AE.

Withdrawal From the Trial. The attending physician will determine, clinically, if a patient should be removed from the trial, stating the reason for the early termination on the appropriate

form. The attending physician will be also responsible for reporting all clinically significant drug related AE. These will be graded on a three-point scale (mild, moderate, severe), and the relationship with the study medication will be assessed as definite, probable, possible, unlikely or no association as defined in the AE form. Any unexpected, life threatening or fatal AE will be reported by telephone within 12 hours after the AE, to the coordinating centre, followed by detailed medical description of the AE, along with copies of all pertinent medical records.

Clinical and laboratory evaluation. Monthly up to 6 months, then every 3 months up to 24 months, then every 6 months up to month 60.

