Statistical Analysis. The values at the final visit for the core set variables will be compared to the baseline values. Furthermore, patients will be dichotomously classified as "responders" or "non-responders" according to the validated JDM definition of improvement. Descriptive statistics will be used for reporting adverse events. For proportional data the chi-square test, or where appropriate the Fisher's exact test, will be applied. For continuous variables the t-test procedure or the ANOVA, will be applied as appropriate. Non parametric ANOVA will be applied in case of ordinal data or not-normally distributed variables; the Dunnett test will be used as a posterior test. Treatment effect size will be calculated by dividing the difference between the baseline and the final visit value, by the standard deviation of the first visit value. Survival analysis with censored data will be used in order to evaluate time to remission and time to flare. Survival curves will be drawn with the Kaplan-Meyer method and compared with the log rank test. For multiple hypothesis testing, alpha level is set at 0.01. Emphasis will be placed on the intention-to-treat approach rather than on analysis of only the completers of the trial. All analysis will be done in a blinded manner.

Table: Time Oriented Table and duration time for each task

| Task No | Months | 1 | 2 | 3 | 4 | 5 | 6 | 7 | 8 | 9 | 10 | 11 | 12 | 13 | 14 | 15 | 16 | 17 | 18 | 19 | 20 |
|---------|--|---|---|---|---|---|---|---|---|---|----|----|----|----|----|----|----|----|----|----|----|
| 1 | Personnel selection and training | | | | | | | | | | | | | | | | | | | | |
| 1 | Translation of material | | | | | | | | | | | | | | | | | | | | |
| 1 | Data base and case report form development | | | | | | | | | | | | | | | | | | | | |
| 1 | Submission to ethics committee | | | | | | | | | | | | | | | | | | | | |
| 2 | Trials enrolment | | | | | | | | | | | | | | | | | | | | |
| 3 | Interim analysis | | | | | | | | | | | | | | | | | | | | |

| Task No | Months | 21 | 22 | 23 | 24 | 25 | 26 | 27 | 28 | 29 | 30 | 31 | 32 | 33 | 34 | 35 | 36 | 37 | 38 | 39 | 40 |
|---------|---------------------------|----|----|----|----|----|----|----|----|----|----|----|----|----|----|----|----|----|----|----|----|
| 2 | Trials enrolment | | | | | | | | | | | | | | | | | | | | |
| 2 | Trial long term follow-up | | | | | | | | | | | | | | | | | | | | |
| 3 | Interim analysis | | | | | | | | | | | | | | | | | | | | |

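### The 15% dropout inflation assumes that dropouts leave the analysis, but the protocol keeps listed dropouts in as failures, so the stated 0.8 and 0.9 power is not established for the emphasised intention-to-treat analysis.

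*Protocol*

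**What the plan says.** The sample size section (Protocol, Sample size calculation for superiority trial) takes its combination-arm rate from an earlier study, where "the observed improvement rate was 83% after 6 months of therapy with PDN combined with MTX or CSA". It estimates 53% for prednisone alone. Its table gives 34 per arm for 0.8 power and 46 for 0.9, both at alpha 0.05, and a last column divides these by 1 − 0.15 to reach 40 and 54. The text reads "Using the sample size calculation for superiority trials and considering a drop out rate of 15%, a sample size of" 40 per group, and continues "The trial will have 0.8 power for comparisons of the combined treatment arms" against prednisone alone. If recruitment is fast, "we will collect 54 patients per arm for a total of 162 patients, 0.9 power, 0.05 type I error".

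The Dropout Criteria, in the same part of the protocol, list two events: non-compliance with study medication and enrolment in another therapeutic trial. Patients with either are classed as treatment failures and are "dropped from the trial but included in efficacy analysis, if any of the following will occur during the active period of the trial". The Statistical Analysis section emphasises intention-to-treat over an analysis of completers.

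The endpoint used for sizing is the responder definition under "Primary Outcome Measures after 6 months of treatment". The test is given as follows: "For proportional data the chi-square test, or where appropriate the Fisher's exact test, will be applied".

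**The concern.** Inflating N by 1/(1 − d) replaces patients who will not be in the analysis. It works if 34 or 46 patients per arm remain and respond at the full 53% and 83%. A patient who is kept and scored as a failure has a different effect: the denominator does not shrink, but both response rates fall, and so does the difference between them. A larger N allows for the first effect and does not restore the difference lost through the second.

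The sizing therefore fits an analysis without the dropouts, while the analysis text points to one that includes at least some of them. The 0.8 and 0.9 are stated without any condition. A reader cannot tell what power 40 or 54 per arm gives for the analysis the protocol emphasises.

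**Working it through.** **Inputs.** From the sample size section: p1 = 0.53, p2 = 0.83, alpha 0.05, power 0.8 and 0.9, dropout 15%, equal arms. Two-sided testing is inferred, because it reproduces both table entries. The protocol names no formula.

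**Step 1: reproduce the table.** Two proportions, unpooled variance, no continuity correction:

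n = (z₀.₉₇₅ + z_power)² × [p1(1−p1) + p2(1−p2)] / (p2−p1)²

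- Variance sum: 0.53×0.47 + 0.83×0.17 = 0.3902.
- Power 0.8: 7.849 × 0.3902 / 0.09 = 34.03 (table: 34).
- Power 0.9: 10.507 × 0.3902 / 0.09 = 45.56 (table: 46).
- Inflation: 34/0.85 = 40.0 and 46/0.85 = 54.1 (table: 40 and 54).

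The arithmetic is right. With dropouts removed, power is 0.800 with 34 analysed and 0.903 with 46.

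**Step 2: keep dropouts as failures.** Assume that a failure is a month-6 non-responder, that 53%/83% hold among patients who stay in, and that a share d of each arm fails. The rates become 0.53(1−d) and 0.83(1−d), and the difference becomes 0.30(1−d). Power by two approximations:

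- Unpooled (matches the table): Φ(Δ / √{[p1(1−p1)+p2(1−p2)]/n} − 1.96).
- Pooled (matches the chi-square test): Φ((Δ − 1.96√{2p̄(1−p̄)/n}) / √{[p1(1−p1)+p2(1−p2)]/n}), with p̄ the mean of the two rates.

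Worked case, d = 0.15, n = 40: rates 0.4505 and 0.7055, Δ = 0.255, variance sum 0.4553, standard error √(0.4553/40) = 0.1067. Then 0.255/0.1067 = 2.390, and Φ(2.390 − 1.960) = 0.67.

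All randomised patients analysed (unpooled / pooled):

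| Failures per arm | Rates | Difference | 40 per arm | 54 per arm |
|---|---|---|---|---|
| 0% | 53.0% v 83.0% | 30.0 | 0.86 / 0.83 | 0.94 / 0.93 |
| 5% | 50.4% v 78.9% | 28.5 | 0.80 / 0.77 | 0.90 / 0.88 |
| 10% | 47.7% v 74.7% | 27.0 | 0.73 / 0.71 | 0.85 / 0.83 |
| 15% | 45.1% v 70.6% | 25.5 | 0.67 / 0.64 | 0.79 / 0.77 |

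The 0% row also covers the case where 53%/83% already count dropouts as failures.

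**Step 3: only part of the 15% are failures and the rest are removed** (unpooled / pooled):

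| Share scored as failures | Analysed per arm | 40 randomised | 54 randomised |
|---|---|---|---|
| One quarter | 35.5 / 47.9 | 0.76 / 0.73 | 0.87 / 0.85 |
| Half | 37.0 / 50.0 | 0.72 / 0.70 | 0.84 / 0.82 |
| Three quarters | 38.5 / 52.0 | 0.69 / 0.67 | 0.82 / 0.80 |

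(In the second column, the first figure is for 40 randomised and the second for 54.)

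**Step 4: break-even.** With everyone else analysed, power equals the stated 0.8 or 0.9 at 4.8% or 5.0% failures (unpooled) and at 2.7% or 3.2% (pooled). The lower pooled values are partly a formula effect: with dropouts removed, pooled power is already 0.767 and 0.882. Measured against those values, the pooled break-even is also about 5%.

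**The case against.** The strongest reply is that the mismatch may be small or absent. The failure rule names two events only. Dropouts for adverse events, by physician decision or through loss to follow-up are outside it, and a history of poor compliance is an exclusion criterion. If most of the 15% simply lack a month-6 assessment and leave the analysis, N/(1 − 0.15) is the ordinary adjustment. The 15% may also refer to the 24-month treatment period, with fewer dropouts by month 6. The earlier study's 83% may already count dropouts. How other missing month-6 data are scored can be left to the statistical analysis plan.

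All of this stands as a limit on the size of the loss. It does not rescue the stated power. The protocol itself fixes the inflation, the failure rule and the emphasis on intention-to-treat, and they do not fit together. Even if only a quarter of the 15% are failures and the rest are removed, power is 0.76 and 0.87 (unpooled). If 53%/83% already count dropouts, power is 0.86 and 0.94, and no inflation was needed.

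Two further points are fair. With unequal dropout, all scored as failures, the effect can go either way: 20% on prednisone alone and 10% on combination gives 0.87 and 0.95 (unpooled), and the reverse gives 0.41 and 0.52. If the two combination arms were pooled against prednisone (2:1), power with 15% failures would be about 0.78 and 0.88 (pooled variance), but the stated N reproduces as a 1:1 comparison.

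**Conclusion.** The concern holds and should be fixed. The table is arithmetically correct, but its dropout adjustment belongs to an analysis without the dropouts. The stated 0.8 and 0.9 are therefore not established for the analysis the protocol emphasises.

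Under equal dropout of up to 15% by month 6, the largest loss takes power to 0.67 (40 per arm) and 0.79 (54 per arm) unpooled, or 0.64 and 0.77 pooled. That is a bound under those conditions and not the expected loss. It rests on two readings that the text does not spell out: that a treatment failure is a month-6 non-responder, which is the natural reading, and that 53%/83% are rates among patients who stay in. The text does not split the 15% by reason or tie it to month 6, so only a range can be given. Every figure is at two-sided 0.05; the 0.01 level that the Statistical Analysis section sets for multiple testing is not applied here.

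**What to change.** In the sample size section and its table:

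1. State that the inflated column assumes dropouts are removed from the analysis.
2. Say whether 53% and 83% already count dropouts as failures.
3. Compute power for the intention-to-treat analysis on failure-imputed rates, with all randomised patients in the denominator, for the dropout assumed by month 6.
4. Replace the single 0.8 and 0.9 with a range that names the formula and the equal-dropout assumption.

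Suggested text: *N/(1−0.15) assumes dropouts are removed from the analysis. With all randomised patients analysed, equal dropout, 53% v 83% among patients who stay in, and 5%, 10% or 15% per arm counted as non-responders by month 6, power at two-sided 0.05 is 0.80, 0.73 or 0.67 (40 per arm) and 0.90, 0.85 or 0.79 (54 per arm) by the unpooled normal approximation, and 0.77, 0.71 or 0.64 and 0.88, 0.83 or 0.77 by the pooled (chi-square) approximation.*

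This changes text and table only and needs no extra patients. The price is a lower stated power, unless month-6 failures are under about 5% (about 3% pooled) with everyone else analysed, or the two rates already count dropouts. Keeping the stated power at 15% failures would be a separate decision about size: by the unpooled formula, 7.849 × 0.4553 / 0.255² = 54.96, so 55 per arm (165 in total) for 0.8, and 10.507 × 0.4553 / 0.255² = 73.6, so 74 per arm (222 in total) for 0.9.
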